#### **7.1.2.6.2 Tumor Imaging During the Study**

Imaging assessments with PET and diagnostic CT scans will be performed after every 4 cycles (12 weeks  $\pm$  7 days) of therapy. Imaging timing should follow calendar days and should not be adjusted for delays in cycle starts. During the first 2 years of the study, imaging should continue to be performed until documented disease progression, the start of new anti-cancer treatment, withdrawal of consent, death, or the end of study, whichever comes first. After 2 years on study, further imaging is to be performed at the discretion of the treating physician. See Section 7.1.2.6.4 for confirmation assessment requirements when a subject's disease response assessment shows an indeterminate response according to the LYRIC response criteria.

#### **7.1.2.6.3 End of Treatment and Follow-up Tumor Imaging**

In participants who discontinue study treatment, tumor imaging should be performed at the time of treatment discontinuation ( $\pm$  4 week window). If previous imaging was obtained within 4 weeks prior to the date of discontinuation, then imaging at treatment discontinuation is not mandatory. In participants who discontinue study treatment due to documented disease progression, no further tumor imaging in the context of this trial is required.

In participants who discontinue study treatment without documented disease progression, every effort should be made to continue monitoring their disease status by tumor imaging using the same imaging schedule used while receiving study treatment (every 12 weeks for up to 2 years) to monitor disease status until the start of a new anticancer treatment, disease progression, pregnancy, death, withdrawal of consent, or the end of the study, whichever occurs first.

#### **7.1.2.6.4 Confirmation Assessments**

Because subjects treated with PD-1 blocking antibodies may have pseudoprogression of disease (there is progression on imaging per conventional response criteria, but the subject is clinically stable or improving), confirmation of progression should be performed in patients having an indeterminate response as defined by the LYRIC criteria (1). Specifically, all patients having an indeterminate response can be continued on therapy at the discretion of the treating investigator. However, repeat imaging must be performed within 12 weeks to either confirm or refute the presence of true disease progression.

Clinical stability may be defined as:

- 1) Absence of symptoms and signs indicating clinically significant progression of disease (including worsening of laboratory values)
- 2) No decline in ECOG performance status
- 3) Absence of rapid progression of disease or progressive tumor at critical anatomical sites (e.g. cord compression) requiring urgent medical intervention

If progression is confirmed on repeat imaging without an intervening response, then the subject will be discontinued from trial treatment, and the initial indeterminate response will be recategorized as disease progression as outlined in the LYRIC criteria (1). If progression is not confirmed, then the subject should continue trial treatment until disease progression is documented following the pre-determined response assessment dates outlined in the Trial Flow Chart (see Section 6.0). Where appropriate, subjects should not be discontinued from study treatment with pembrolizumab until progression is confirmed. However, the decision to continue or discontinue study treatment in the case of an intermediate response is that of the treating physician.

#### **7.1.2.6.5 Tumor Tissue Collection and Correlative Studies Sampling**

All subjects enrolled into this study must be able to provide an archived FFPE biopsy sample or preferably a newly-obtained core needle or excisional biopsy (FNA is not adequate) to be submitted for characterization through the research collaborations organized by the principal investigator.

Serial blood and baseline stool specimens will be collected as documented in the Trial Flow Chart (Section 6.0) for additional exploratory analyses. The specific protocols for collecting serial blood and baseline stool samples is outlined in greater detail in the accompanying lab manual. Briefly however, blood will be compartmentalized into plasma, serum, and peripheral blood mononuclear cells on-site within 2 hours of sample collection and will be shipped to The University of Chicago Human Tissue Resource Center for long-term storage. Germline DNA will also be extracted from peripheral blood to provide a paired normal reference for tumor whole exome sequencing. Correlative blood samples should be obtained at the time of routine blood specimens drawn for the main trial whenever possible. Baseline stool sampling will be obtained using a home stool collection kit. Once stool has been collected at home, the kit can either be returned by the patient at their next clinic appointment or shipped directly to The University of Chicago Microbiome Core Facility using the attached return address information.

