### 3.3 Exploratory Objectives

- (1) **Objective:** To compare the immune landscape of DLBCLs with and without *PD-L1* gene alterations (non-*PD-L1* gene-altered DLBCLs will consist of previously identified patient samples stored in The University of Chicago Lymphoma Biobank).
- (2) **Objective:** To compare gene expression signatures of DLBCLs with and without *PD-L1* gene alterations.
- (3) **Objective:** To compare genomic mutational profiles and neo-antigen load of DLBCLs with and without *PD-L1* gene alterations.
- (4) **Objective:** To determine whether the degree of *PD-L1* gene alterations in DLBCL (amplified = translocated > relative copy gain > polysomy) correlates with response and survival to pembrolizumab.
- (5) **Objective:** To determine the impact of PD-L1 protein expression as assessed by immunohistochemistry (IHC) (both on malignant tumor cell and within the tumor microenvironment using Dako PD-L1 IHC 22C3 pharmDx)) on the ORR to pembrolizumab treatment in patients with *PD-L1* gene-altered DLBCLs.
- (6) **Objective:** To compare the intestinal microbiota diversity and composition between DLBCL patients with and without *PD-L1* gene alterations, and to determine if the composition and/or diversity of the host microbiome predicts for response to pembrolizumab in *PD-L1* gene-altered DLBCL patients.
- (7) **Objective:** To identify the feasibility of monitoring clonal tumor evolution in response to pembrolizumab using ctDNA, and to determine the utility of measuring ctDNA burden in predicting clinical outcomes (PFS, DOR, OS) following pembrolizumab treatment.

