**4.2.3.2.2 Effect of tumor cell intrinsic and environmental factors on responsiveness to pembrolizumab in DLBCL.** Previous studies have demonstrated an impact of both tumor cell intrinsic and environmental factors, as well as other host variables, such as the intestinal microbiome, on responsiveness to anti-PD-1 therapies in a variety of solid tumor malignancies (46-48). To determine whether these features also influence responsiveness to PD-1 blockade in DLBCL, whole exome sequencing (WES) and RNA sequencing (seq) will be performed on pre-treatment biopsies, and baseline stool samples will be collected prior to commencing study therapy with pembrolizumab. WES of tumor samples will be performed through Theragen Etex, while RNA-seq, bioinformatics analysis, and microbiome analysis will all be conducted in core facilities at The University of Chicago.

**4.2.3.2.3 Feasibility of utilizing circulating tumor DNA (ctDNA) to predict early response to pembrolizumab in DLBCL, and to identify genetic mechanisms that underlie acquired resistance to therapy.** The quantification of ctDNA can be a sensitive marker of response to a wide array of therapies in a number of tumor types while also providing valuable prognostic information (49, 50). Furthermore, ctDNA offers a non-invasive method of serially monitoring the clonal evolution of tumors responding to a particular therapy, and may also identify mutations or other genomic alterations associated with emerging resistance. Currently, there are no data on the use of ctDNA to monitor response, clonal evolution or resistance to anti-PD-1 therapy, and the mechanisms of acquired resistance to pembrolizumab in DLBCL are unknown. To investigate the hypothesis that serial ctDNA monitoring will provide early response information to pembrolizumab, and will identify mutations in genes critical for maintaining immune surveillance in patients developing acquired resistance to therapy, plasma will be collected for ctDNA analysis at baseline and after every 4 cycles of therapy (in parallel with disease response assessment via conventional imaging). All ctDNA analyses will be performed using a customized lymphoma panel created at the Cancer Precision Medicine Center in the Cancer Institute of Japanese Foundation for Cancer Research.

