- a.  $\geq 2$  lines of prior systemic therapy
- b.  $\geq 1$  line of prior systemic therapy with documented comorbidities that preclude eligibility for standard salvage chemotherapy and autologous stem cell transplant , or
- c. 1 line of prior therapy with documented disease relapse within 12 months of initial diagnosis.

*Note: patients having undergone prior CAR T cell therapy are eligible, as are patients having received a prior allogeneic transplantation, provided they do not meet any of the exclusionary GVHD criteria, and are at least 5 years removed from the date of their transplant.*

9. Have an Eastern Cooperative Oncology Group (ECOG) performance status of 0 to 1. Evaluation of ECOG performance status is to be performed within 14 days prior to the date of treatment allocation.

10. Have adequate organ function as defined in Table 1 within 10 days prior to the date of treatment allocation.

Table 1. Adequate Organ Function Laboratory Values

System	Laboratory Value
Hematological	
Absolute neutrophil count (ANC)	$\geq 1,000/\mu\text{L}$

Platelets	$\geq 50,000/\mu\text{L}$
Hemoglobin	$\geq 8.0 \text{ g/dL}^a$
Renal	
Creatinine OR Measured or calculated b creatinine clearance (GFR can also be used in place of creatinine or CrCl)	$\leq 1.5 \times \text{ULN}$ OR $\geq 30 \text{ mL/min}$ for participant with creatinine levels $> 1.5 \times \text{institutional ULN}$
Hepatic	
Total bilirubin	$\leq 1.5 \times \text{ULN}$ OR direct bilirubin $\leq \text{ULN}$ for participants with total bilirubin levels $> 1.5 \times \text{ULN}$
AST (SGOT) and ALT (SGPT)	$\leq 2.5 \times \text{ULN}$ ( $\leq 5 \times \text{ULN}$ for participants with liver metastases)
Coagulation	
International normalized ratio (INR) OR prothrombin time (PT)	$\leq 1.5 \times \text{ULN}$ unless participant is receiving anticoagulant therapy as long as PT or aPTT is within therapeutic range of intended use of anticoagulants
Activated partial thromboplastin time (aPTT)	

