8. Is currently participating in or has participated in a study of an investigational agent or has used an investigational device within 4 weeks prior to the first dose of study treatment.
9. Has a diagnosis of immunodeficiency or is receiving chronic systemic steroid therapy (in dosing exceeding 10 mg daily of prednisone equivalent) or any other form of immunosuppressive therapy within 7 days prior to the first dose of study drug. Short courses of corticosteroids will be allowed for palliation of symptoms related to lymphoma, but must be discontinued within 7 days prior to the first dose of study drug.
10. Subjects having received prior allogeneic stem cell transplant, must be at least 5 years removed from the date of their transplant. The also must have no history of severe (grade 3-4) acute GVHD, and/or current > grade 1 acute GHVD. Subjects must not have active chronic GVHD that requires active immune suppression or more than 10 mg of prednisone/day or equivalent.
11. Has a history of a solid organ transplant.
12. Has a known additional malignancy that is progressing or has required active treatment within the past 3 years. Note: Participants with basal cell carcinoma of the skin, squamous cell carcinoma of the skin, or carcinoma in situ (e.g. breast carcinoma, cervical cancer in situ) that have undergone potentially curative therapy are not excluded
13. Has severe hypersensitivity ( $\geq$ Grade 3) to pembrolizumab and/or any of its excipients.
14. Has active autoimmune disease that has required systemic treatment in the past 2 years (i.e. with use of disease modifying agents, corticosteroids or immunosuppressive drugs).

Replacement therapy (eg., thyroxine, insulin, or physiologic corticosteroid replacement therapy for adrenal or pituitary insufficiency, etc.) is not considered a form of systemic treatment.

15. Has a history of (non-infectious) pneumonitis that required steroids or has current pneumonitis.
16. Has an active infection requiring systemic therapy.
17. Has a known history of Human Immunodeficiency Virus (HIV) infection.
18. Has a known history of Hepatitis B (defined as Hepatitis B surface antigen [HBsAg] reactive) or known active Hepatitis C virus (defined as detection of HCV RNA) infection.
19. Has a known history of active TB (Bacillus Tuberculosis).

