#### **c. Biomedical Research Specimen Collection**

Serial blood, baseline stool, and archival biopsies will be collected as documented in the Trial Flow Chart (Section 6.0). All blood specimens will be obtained at a time when the subject is having blood drawn for other trial purposes. Baseline stool will be collected by the patient using a home stool collection kit.

The protocol for serial blood and baseline stool collection is outlined in more detail in the accompanying lab manual. Briefly, blood will be compartmentalized into plasma, serum, and peripheral blood mononuclear cells at the patient's trial site within 2 hours of sample collection and will be shipped to The University of Chicago Human Tissue Resource Center for long-term storage. Germline DNA will also be extracted from peripheral blood to provide a paired normal reference

for tumor whole exome sequencing. More detailed information regarding the specific reagents and blood processing techniques is provided in the accompanying lab manual. Subjects participating in the study will be provided a home stool collection kit for baseline stool sampling. After stool collection, the kit can either be returned by the patient at their next clinic appointment or shipped directly to The University of Chicago Microbiome Core Facility using the attached return address information.

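### Blood is the only germline reference named for tumour exome sequencing, yet prior allogeneic transplant recipients may enrol; in recipient-origin lymphoma with donor blood formation, inherited variants would be miscalled as somatic

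*Combined protocol and SAP*

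**What the plan says.** Section 7.1.2.6.5 names the reference sample: "Germline DNA will also be extracted from peripheral blood to provide a paired normal reference for tumor whole exome sequencing". Appendix 6, part 2c, says the same: "Germline DNA will also be extracted from peripheral blood to provide a paired normal reference". No group of patients is excepted in either place. Both sections are summaries and refer to a lab manual for detail.

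The tumour side is set in section 4.2.3.2.2: "whole exome sequencing (WES) and RNA sequencing (seq) will be performed on pre-treatment biopsies". The result serves exploratory objective 3 in section 3.3, "To compare genomic mutational profiles and neo-antigen load of DLBCLs" with and without *PD-L1* gene alterations. Section 4.2.3.2.2 also uses it to relate tumour-intrinsic features to response.

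On eligibility, the note to inclusion criterion 8 (section 5.1.1) accepts patients after CAR T-cell therapy, "as are patients having received a prior allogeneic transplantation, provided they do not meet any of the exclusionary GVHD criteria". Exclusion criterion 10 (section 5.1.2) adds the time limit: "Subjects having received prior allogeneic stem cell transplant, must be at least 5 years removed from the date of their transplant".

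Section 7.1.3.2 lists the correlative specimens as blood and plasma, FFPE lymph node tissue, and stool. No non-haematopoietic normal, pre-transplant sample, donor sample or chimerism test is mentioned. Section 8.2.5.1 has no rule for transplant recipients in the genomic analyses.

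**The concern.** A paired normal is meant to show which variants the patient was born with, so that subtracting it from the tumour leaves the acquired ones. After an allogeneic transplant with donor engraftment, the DNA in blood cells is wholly or mainly the donor's. It then describes the wrong person. More blood or deeper sequencing would not help, because the fault lies in the reference and not in its precision.

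The protocol admits this group deliberately and sets conditions for it, so the rule fails for patients the plan foresees. At stake is the validity of the mutation-load and neo-antigen-load values for any such patient. Under objective 1 of section 3.3 the unaltered comparison samples come from a biobank, so the trial's own patients supply the *PD-L1*-altered side. An error in them falls on that side and could mimic or mask a difference. It could also distort the relation of load to response in a cohort of at most 29.

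**Working it through.** The plan states no figure on this point. The only planned numbers used are the cohort sizes in section 8.1.3: 13 patients in stage 1 and a maximum of 29.

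**Step 1: the passages side by side.**

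| Question | What the documents give |
|---|---|
| Which normal is used? | Peripheral blood, no exception (7.1.2.6.5; Appendix 6, 2c) |
| Can allogeneic recipients enrol? | Yes, at least 5 years out and within the GVHD limits (5.1.1; 5.1.2) |
| Is another normal collected? | None listed (7.1.3.2) |
| Is there an analysis rule for them? | None (8.2.5.1) |
| Which results depend on it? | Objective 3 (3.3) and the analyses of 4.2.3.2.2 |

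**Step 2: which variants are miscalled.** Assume donor blood formation and a recipient-origin tumour.
- Carried by both recipient and donor: present in tumour and blood, correctly removed.
- Carried by the donor only: present in blood only, not called somatic.
- Carried by the recipient only: present in tumour but not in blood, wrongly called somatic. Coding variants among these can enter neo-antigen prediction.

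Write S for the true somatic count and R for the recipient-only inherited variants that survive filtering. The apparent load is S + R, and the inflation factor is m = (S + R)/S. R is smaller with a related donor, with mixed chimerism, or if known inherited variants are filtered out. If the lymphoma is donor-derived, this bias does not arise. The documents give neither S nor R, nor the calling and filtering rules.

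**Step 3: illustration of the effect on a mean.** Suppose k of n patients are affected, each by a factor m, and all patients have the same true load. Then

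mean ratio = ((n − k) + k·m)/n.

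The values of k and m are assumptions.

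| n | k | m = 10 | m = 100 |
|---|---|---|---|
| 29 | 0 | 1.00 | 1.00 |
| 29 | 1 | (28 + 10)/29 = 1.31 | (28 + 100)/29 = 4.41 |
| 29 | 2 | (27 + 20)/29 = 1.62 | (27 + 200)/29 = 7.83 |
| 13 | 1 | (12 + 10)/13 = 1.69 | (12 + 100)/13 = 8.62 |
| 13 | 2 | (11 + 20)/13 = 2.38 | (11 + 200)/13 = 16.23 |

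If m is close to 1, the ratio is close to 1 whatever k is.

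**Step 4: whether any such patient enrols.** The documents give no prevalence. If 1% of enrolled patients were allogeneic recipients (an assumption), the chance of at least one would be 1 − 0.99^29 = 25% in 29 patients and 1 − 0.99^13 = 12% in 13. At zero prevalence the point has no effect.

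**The case against.** The strongest reply is that this is a narrow, conditional problem in exploratory work. Much of that stands.

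- **It may never arise.** No allogeneic recipient may enrol. If one does, the bias needs predominantly donor blood formation and a recipient-origin tumour. A reader might infer that load will be falsely high in every transplant recipient; the documents do not support that.
- **Its size is unknown.** A reader might count every donor–recipient difference as a false call and arrive at a very large inflation. Only recipient-only variants count, and the documents describe no calling or filtering rules from which a figure could be derived.
- **A mean is not a planned analysis.** Section 8.2.5.1 names Fisher's exact test, Wilcoxon tests (for PD-L1 protein expression) and Cox models for other biomarkers. In a rank test one extreme value counts as one rank. But the section assigns no method to mutation or neo-antigen load, and a Cox model with untransformed load could be sensitive to an outlier.
- **It can be handled at analysis.** A reader might think the data are lost unless action is taken at entry. That goes too far. Section 7.1.1.5.2 has all prior cancer treatments reviewed, and the eligibility criteria require the transplant date and GVHD history to be checked, so the patient can be identified and excluded later.
- **The lab manual may hold an exception.** It is not among the documents, so this cannot be ruled out.

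None of this corrects the reference that the protocol names. An exclusion decided only after an extreme value is seen is also weaker than one set in advance.

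**Conclusion.** The point holds in conditional form, and it is minor. The protocol names one reference sample without exception and admits a group for whom that sample can be the wrong person's DNA. For a recipient with predominantly donor blood formation and recipient-origin lymphoma, following the rule as written would inflate mutation and neo-antigen load.

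The size depends on the number of such patients, donor relatedness, chimerism and variant filtering, none of which the documents give. The illustrative ratios of 1.3 to 4.4 (one patient in 29) rest wholly on the assumed 10- to 100-fold inflation, and the true effect may be nil. ORR, PFS, DOR, OS, safety and the sample size are unaffected.

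**What to change.** In section 7.1.2.6.5 and in Appendix 6, part 2c, add that peripheral blood is not used as the paired normal for patients with a prior allogeneic transplant. Already stored pre-transplant recipient DNA or uninvolved archival tissue is used instead, if it exists and consent covers it. Otherwise the patient is excluded from the mutation-load and neo-antigen-load analyses. Identify these patients from the transplant history already recorded at eligibility and prior-treatment review, and bring the lab manual into line.

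The cost is a sentence in two places, with no new visit or sampling procedure and no change to eligibility or treatment. Consent needs checking, because Appendix 6, part 2b, covers archival biopsies, blood and stool and does not mention retrieval of older stored DNA. The downside is that any such patient may drop out of these exploratory analyses.

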#### **7.1.3 Laboratory Procedures/Assessments**

Details regarding specific laboratory procedures/assessments to be performed in this trial are provided below.

##### **7.1.3.1 Laboratory Safety Evaluations (Hematology, Chemistry, and Urinalysis)**

Laboratory tests for hematology, chemistry, urinalysis, and others are specified in Table 5.

Table 5. Laboratory Tests

Hematology	Chemistry	Urinalysis	Other
Hematocrit	Albumin	Blood	Serum $\beta$ -human chorionic gonadotropin†
Hemoglobin	Alkaline phosphatase	Glucose	( $\beta$ -hCG)†
Platelet count	Alanine aminotransferase (ALT)	Protein	Thyroid stimulating hormone (TSH)
WBC (total and differential)	Aspartate aminotransferase (AST)	Specific gravity	Blood for correlative studies
Red Blood Cell Count	Lactate dehydrogenase (LDH)	Microscopic exam ( If abnormal )	
Absolute Neutrophil Count	Carbon Dioxide ‡	Urine pregnancy test †	
Absolute Lymphocyte Count	( CO2 or biocarbonate )		
	Uric Acid		
	Calcium		
	Chloride		
	Glucose		
	Potassium		
	Sodium		
	Total Bilirubin		
	Direct Bilirubin ( If total bilirubin is elevated above the upper limit of normal )		
	Total protein		
	Blood Urea Nitrogen		

† Perform on women of childbearing potential only. If urine pregnancy results cannot be confirmed as negative, a serum pregnancy test will be required.

‡ If considered standard of care in your region.

Laboratory tests for the initial screening phase should be performed within 10 days prior to the first dose of treatment. After cycle 1, pre-dose laboratory procedures can be conducted up to 72 hours prior to dosing. Results must be reviewed by the investigator or qualified designee and found to be acceptable prior to each dose of trial treatment.

